9.3. Outcome Status

Outcomes are based on WHO's reporting framework for tuberculosis in 2020 (39).Treatment outcome definitions have recently been revised by WHO and will be updated in the 2021 revision of WHO's *Definitions and reporting framework for tuberculosis*. Once this guideline becomes available and the new definitions are adopted for programmatic implementation, the protocol will be updated (<https://www.who.int/publications/i/item/9789240022195>).

Table 7: Treatment outcomes for RR-TB/MDR-TB/XDR-TB participants treated

Outcome	Definitions per TRiAD Protocol	2021/2022 WHO Definitions
Cured	Treatment completed as recommended by the national policy without evidence of failure AND three or more consecutive cultures taken at least 30 days apart are negative after the intensive phase	A pulmonary patient with bacteriologically confirmed DR-TB at the beginning of treatment who completed the recommended treatment , with evidence of bacteriological response* and no evidence of failure
Treatment completed	Treatment completed as recommended by the national policy without evidence of failure BUT no record that three or more consecutive cultures taken at least 30 days apart are negative after the intensive phase	A patient who completed treatment as recommended and who does not meet the definition of cure or treatment failure
Treatment failed *	Treatment terminated or need for permanent regimen change of at least two anti-TB drugs because of: 
 - lack of conversion by the end of the intensive phase, or - bacteriological reversion in the continuation phase after conversion to negative, or - evidence of additional acquired resistance to fluoroquinolones or second-line injectable drugs, or - adverse drug reactions (ADRs) 	A patient whose treatment regimen needed to be terminated or permanently changed to new regimen or treatment strategy. Reasons for change include : 
 - No clinical and or bacteriological response - Adverse drug reaction/s - Evidence of additional drug resistance to medicines in the regimen
Died	A participant who dies for any reason during the course of treatment.	A patient who died for any reason during treatment
Lost to follow-up	A participant whose treatment was interrupted for 2 consecutive months or more.	A patient with treatment interrupted for ≥ 2 consecutive months for any reason without medical approval
Not evaluated	A participant for whom no treatment outcome is assigned. (This includes cases “transferred out” to another treatment unit and whose treatment outcome is unknown)	A patient recorded in the register and who does not have the necessary recorded data to enable classification of any outcome
Treatment success	The sum of cured and treatment completed	Is sum of cured and treatment completed

Sustained treatment success (optional outcome)		A patient assessed at 6 months and at 12 months after successful TB treatment, who is alive and free of TB.
--	--	---

*For treatment failed, lack of conversion by the end of the intensive phase implies that the participant does not convert within the maximum duration of the intensive phase applied by the programme. If no maximum duration is defined, an 8-month cut-off is proposed. For regimens without a clear distinction between intensive and continuation phases, a cut-off 8 months after the start of treatment is suggested to determine when the criteria for *Cured*, *Treatment completed* and *Treatment failed* start to apply.

The terms “conversion” and “reversion” of culture results are defined as follows:

- **Conversion** (to negative): culture is considered to have converted to negative when two consecutive cultures taken at least 30 days apart are found to be negative. In such case, the specimen collection date of the first negative culture is used as the date of conversion.
- **Reversion** (to positive): culture is considered to have reverted to positive when after an initial conversion, two consecutive cultures taken at least 30 days apart are found to be positive.

“Recurrent TB” is defined as being either of the following circumstances after cure or completion of treatment:

- Two consecutive positive cultures, or
- One positive culture with clinical signs and symptoms or radiographic deterioration (an isolated positive smear or culture without clinical or radiographic deterioration after treatment completion provides insufficient evidence to define recurrent TB).

If genotyping is available, recurrent TB may be further classified as relapse, reinfection, or undetermined as defined below:

- **Relapse**: isolates of the recurrent episode share the same genotype pattern with isolates of the first episode of MDR-TB.
- **Reinfection**: isolates of the recurrent episode and isolates of the first episode of MDR-TB have different genotype patterns.
- **Undetermined**: there is insufficient information to determine whether the recurrent episode is due to relapse or reinfection.

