6.2.3. Selection of Historical Cohorts

Each CRS will build a dataset of historical RR-TB participants that were diagnosed and started on treatment within 12 - 18 months prior to starting enrolment of the study at each of the clinical research sites. Clinical and laboratory data from this retrospective cohort will be obtained from treatment registers, participant charts and laboratory databases at each of the clinical research sites. The following data variables will be extracted: date of birth, or age, sex, HIV and ART status, facility or clinic, year and month of treatment, type of DR-TB, certainty of diagnosis (confirmed by DST or presumed, i.e., contact of DR-TB source case or failing adherent first-line TB treatment), disease classification, treatment start date and any bacteriological results on treatment (date, mycobacterial culture, DST and genotypic results), where relevant. Data on all drugs from previous DR-TB treatment regimen, DR-TB Outcomes: cure, completion, default, death, loss to follow up (LTFU) will be abstracted. Historical data will be collected on specially designed case report forms (CRF) and will be subject to routine quality assurance/control QA/QC of data to ensure maximum quality. Bias by time period and by other confounders such as HIV, gender and age, will be controlled for in the analysis. No historical data will be generated for cohort 2, as no routine data on HR-TB is available.

6.3. Participant Inclusion Criteria for cohorts 1 and 2

1. Ambulant adults \geq 18 years of age
2. Newly diagnosed PTB patients receiving less than 5 days of treatment since new diagnosis:
 - a) Cohort 1: < 5 days of DR-TB treatment
 - b) Cohort 2: < 5 days of INH mono-resistant TB treatment preceding study entry for the current TB episode, or
3. Sputum positive (smear and or culture) TB patients classified as failing first line treatment
4. Any currently available Nucleic Acid Amplification Tests for drug-resistance detection changes/assay positive for M.tb infection with:
Cohort 1: at least Rifampicin resistance

- Cohort 2: Rifampicin susceptible co-occurring with INH, fluoroquinolone, ethionamide or aminoglycoside resistance (detected by Xpert XDR) occurring alone or in combination
5. Capacity to provide informed consent
 6. HIV infected and uninfected participants are allowed in the study. Participants already on ART will be allowed in the study provided the ART regimen in use has no contraindications to the proposed TB drug regimen

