The estimated XDR prevalence among MDR cases is 4.3% in South Africa (2018 Global TB report), 0.6% and 0.7% in Nigeria and Ethiopia (2019 Global TB report). This would mean that N=880*4.3% = 38 XDR cases. As BPaL eligibility extends to pre-XDR patients and treatment intolerant MDR patients, it is expected that a higher number will be on BPaL. A total of 40 participants (including 15% LFU) are needed to detect an improvement from 53% to 85%. This number should be possible for all sites together. Assuming approx. 10% HR-TB in each site, we aim to enrol N=400 in cohort 2 which would allow for approximately 100 HR-TB participants per site, which should be sufficient for studying associated secondary study outcomes.

9.2. Analysis including statistical methods:

Primary endpoint analysis:

- The time to appropriate treatment initiation will be calculated as median days (with interquartile range) between the first sputum collection date and the date of start of the regimen appropriate to the drug resistance pattern (defined as drug-resistance pattern appropriate treatment). This will be compared to the same time in the historical cohort and stratified by geographical location (study site). Confounding will be addressed by multivariable analysis.
- The proportion of favourable study outcomes [treatment cure or completion, based on the WHO definitions (5) will be calculated in the overall study population of cohort 1, and compared with the same proportion in the historical cohort, and stratified by geographical location (study site). In a secondary analysis, these proportions will also be calculated per type of DR-TB. Confounding will be addressed by multivariable analysis.

Both of these outcomes will only be calculated in the primary cohort (cohort 1), as no reliable historical data exist for either endpoint for HR-TB (cohort 2).

Secondary endpoint analysis:

- Prevalence of HR-TB stratified by geographical location. This will be calculated in cohort 2 and stratified by HIV status.
- The incidence of adverse events will be divided into adverse events and serious adverse events and calculated in proportions using both cohort 1 and 2. These will also be stratified by type of DR-TB, treatment regimen, and HIV status.
- Feasibility and acceptability (participant and health care provider perspective), stratified by type of DR-TB regimen (cohort 1 and 2)

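### The failure definition in force does not cover acquired resistance to bedaquiline, linezolid or pretomanid, and no rule fixes one outcome definition for cohort 1 and the historical cohort

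*Protocol*

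**What the plan says.** Section 4.5 makes the proportion with a favourable outcome a primary outcome and sends the reader to Section 9.3 for its definition. Section 9.3 puts one framework in force: "Outcomes are based on WHO's reporting framework for tuberculosis in 2020". Table 7 then prints two columns, the protocol's definitions and the WHO 2021/2022 definitions.

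In the protocol's column, failure needs an entry condition, "Treatment terminated or need for permanent regimen change of at least two anti-TB drugs because of", and one of four reasons: no conversion by the end of the intensive phase, reversion, adverse drug reactions, or the resistance ground, "evidence of additional acquired resistance to fluoroquinolones or second-line injectable drugs, or". In the WHO 2021/2022 column the resistance ground reads "Evidence of additional drug resistance to medicines in the regimen", and the entry condition has no two-drug count.

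On future changes, Section 9.3 says: "Once this guideline becomes available and the new definitions are adopted for programmatic implementation, the protocol will be updated".

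Section 9.2 says the cohort 1 proportion will be "compared with the same proportion in the historical cohort". Section 6.2.3 describes the source of the historical outcomes: "DR-TB Outcomes: cure, completion, default, death, loss to follow up (LTFU) will be abstracted". The same section also collects drugs and, where relevant, culture, DST and genotypic results.

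**The concern.** The resistance ground in force suits regimens built on a fluoroquinolone or an injectable. Table 2 proposes a bedaquiline-based all-oral regimen or BPaL for cohort 1. For pre-XDR and XDR participants on BPaL the ground is nearly empty: by the Section 3 definitions they already have fluoroquinolone resistance, and BPaL contains no injectable.

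The event that is missed is one the protocol expects. Section 8.2 foresees that resistance found after the start of treatment may lead to a regimen being modified, extended or stopped. Section 4.4.2 sets out to measure bedaquiline and linezolid resistance that calls for a switch.

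At stake is the comparison of favourable outcomes between cohort 1 and the historical cohort. If the two are classified by different rules, or by one rule that fits one cohort's regimens better, part of any difference reflects coding and not treatment.

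**Working it through.** **Step 1: one participant, two columns.** Take a cohort 1 participant on BPaL with no non-conversion, reversion or adverse reaction. At least two drugs are permanently changed because of acquired bedaquiline and linezolid resistance, and the modified treatment is completed.

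| Element | Protocol column | WHO 2021/2022 column |
|---|---|---|
| Entry condition | Met (two drugs changed) | Met if the change amounts to a new regimen or strategy |
| Resistance reason | Not met: neither drug is a fluoroquinolone or injectable | Met: both drugs are in the regimen |
| Failure | No listed reason applies | Yes |
| Possible outcome | Completed (or cured, with enough negative cultures), so favourable | Failed, so unfavourable |

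If only one drug is replaced, the protocol column's two-drug condition is not met either.

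**Step 2: what happens when definitions change.** Section 9.3 promises a protocol update. It does not say whether participants already classified are re-coded, whether the new set applies only to later enrolments, or whether the historical cohort moves too. Historical outcomes are abstracted as recorded categories, with no stated definition behind them. Section 9.2 asks for the same proportion in both cohorts, but nothing ties both to one column.

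**Step 3: size, as an illustration only.** The protocol states no acquired-resistance rate, so there is no plan figure to reproduce. Let x1 and x0 be the shares of cohort 1 and of the historical cohort that one column calls favourable and the other calls failed. The distortion of the comparison is x1 − x0.

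Inputs from Section 9.1: n = 220 per study site, 15% loss to follow-up, planned difference 74% to 85% = 11 points. Evaluable per group: 220 × 0.85 = 187. Assumptions: equal groups, two-sided alpha 0.05 (Section 9.1 states none), true success of 74% in both groups, x0 = 0.

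For an assumed x1 = x, with p1 = 0.74 + x and p̄ = 0.74 + x/2:

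- SE0 = √(2·p̄(1 − p̄)/187) and SE1 = √((0.74·0.26 + p1(1 − p1))/187)
- chance of a significant result favouring cohort 1 = Φ((x − 1.96·SE0)/SE1)

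| Assumed x | Participants of 880 | Share of the 11 points | Chance of a false result favouring cohort 1 (nominal 2.5%) |
|---|---|---|---|
| 1% | 880 × 0.01 ≈ 9 | 1/11 = 9% | 4.1% |
| 2% | 880 × 0.02 ≈ 18 | 2/11 = 18% | 6.5% |
| 3% | 880 × 0.03 ≈ 26 | 3/11 = 27% | 9.9% |
| 5% | 880 × 0.05 = 44 | 5/11 = 45% | 20.6% |

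These rows show how the endpoint responds to x. They do not estimate x.

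**The case against.** The strongest objection is that an event missing from the failure list is not thereby a success. Both favourable categories require treatment to be completed as national policy recommends and without evidence of failure, and a participant with no assigned outcome is not evaluated, which is also unfavourable. The primary objective looks at month 12, while the long regimens in Table 2 with stated durations run 18 to 20 months (for example 6 + 12 and 6 + 14), so many switched participants could not have completed by then. This stands. It confines the misclassification to participants whose regimen is modified or extended and who still complete in time.

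Other points also stand in part:

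- Levofloxacin and moxifloxacin are oral study drugs (Table 9), and fluoroquinolone resistance is named. The gap concerns bedaquiline, linezolid and pretomanid, not all oral study drugs.
- Non-conversion and reversion will catch some resistant participants. The backstop is partial: for regimens without distinct phases the Table 7 footnote suggests 8 months as the point from which outcomes apply, and Section 8.1 puts BPaL at 24 weeks.
- Section 6.5 makes resistance to BPaL drugs on post-enrolment testing a late exclusion. It does not say how such participants count in the endpoint, and Section 6.2.3 gives no counterpart for the historical cohort.
- Table 2 lists bedaquiline and linezolid in several current regimens, so the omission can affect historical patients too. Then x0 is above zero and the net distortion is smaller than in the table.
- The missing failed and not-evaluated labels in the historical list do no harm if those patients stay in the denominator. Nothing says they are dropped, and nothing says they are kept.

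It can also be said that the rule for applying definitions belongs in a statistical analysis plan, which is not at hand. That does not answer the point in full: the protocol itself states the operative rule, prints a conflicting one beside it and announces a change.

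**Conclusion.** The point holds in a limited form. The definition in force omits acquired resistance to bedaquiline, linezolid and pretomanid as a ground for failure. The adjacent column includes it, and no passage fixes which set governs both cohorts once definitions are updated. Only the favourable-outcome endpoint is affected; time to treatment initiation does not use Table 7.

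A reader might infer that the two cohorts are already on different scales, or that every participant with such resistance will be counted as a success. The protocol supports neither. Section 9.2 calls for the same proportion in both cohorts, and many of these participants would be unfavourable on other grounds. A reader might also take 5 points of the planned 11 as an expected bias. That figure rests on an assumed 5% with no anchor in the protocol, and on every such participant moving from failed to favourable with no offset in the historical cohort.

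What can be said is that each 1% of cohort 1 reclassified, net of the historical cohort, moves the difference by 1 point against a planned 11. The true size is unknown and could be small.

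**What to change.** Before analysis, name one Table 7 definition set for the primary analysis of cohort 1 and the historical cohort, with a failure ground that covers resistance to any drug in the regimen. State that later programme changes do not alter the primary endpoint; outcomes under a newer set can be reported as secondary.

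Apply the same set to the historical cohort from the abstracted culture, DST and drug data where these exist, and add a sensitivity analysis using outcomes as recorded. Add failed and not evaluated to the historical abstraction list, so that these patients are visibly kept in the denominator.

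The cost is protocol wording, two more abstraction codes and some re-coding of historical outcomes. The main drawback is that historical resistance data are collected only where relevant and may be incomplete, so re-derivation may be partial. The sensitivity analysis would show how much that matters.

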10. PROCEDURES FOR ASSESSING SAFETY AND ADVERSE EVENT REPORTING

10.1. Adverse Events (AEs) and Adverse Event Reporting

An AE is defined as any untoward medical or social occurrence in a clinical research participant that may or may not have a causal relationship with the study drugs/interventions. The principles of ICH GCP require that investigators follow specific procedures when notifying adverse events or reactions in clinical trials.

Adverse drug reaction (ADR): is defined as a response to a medicine in humans that is noxious and unintended, including lack of efficacy, and that occurs at doses normally used in man and that can also result from overdose, misuse or abuse of a medicine. All adverse events judged by either the investigator as having a reasonable causal relationship to a medicinal product qualify as adverse reactions. ADRs that occur following enrolment will be considered AEs and will be recorded on the AE CRF.

Unexpected Adverse Reaction (UAR): is a reaction in which the nature, specificity, severity and outcome is not consistent with the approved package insert for a registered medicine (or investigator's brochure for an investigational product). When the outcome of the adverse reaction is not consistent with the applicable product information, this adverse reaction should be considered as unexpected. UARs that occur following enrolment will be considered AEs and will be recorded on the AE CRF.

Clinical AEs grade 3-5 will be recorded via the AE recording CRF. The clinical course of each grade 3 and 4 event should be followed until resolution, stabilization, or until it has been determined that the study treatment is not the cause. All participants reporting an AE will be followed clinically, until the AE resolves (returns to baseline/non-gradable range). AEs that are ongoing at the time of study exit will be followed up for up to 30 days after study exit and then, if not resolved, will be referred to a health care provider for further follow-up.

The Principal Investigator (PI) or designee must determine the severity of the AE and document it on the appropriate CRF (AE Form). Generally if toxicity occurs on any of the drugs used in the study, the decision on whether to continue or stop the drug will depend on severity of the toxicity, duration of treatment received, whether the participant has culture converted, how many other active drugs are in regimen, how essential the drug is to the regimen and whether it can be replaced with another active drug. Each decision will be decided upon by the attending clinician. Severity does not have the same meaning as seriousness, since a participant can experience a severe event such as a skin rash that is not serious. Grading is subjective, based upon perspective of the attending clinician and participant. Additionally, especially for measurements and laboratory results, grading may differ according to age, gender, body mass index (BMI) and weight.

Table 8: Grading the severity of ADR; following common guidelines and management for the treatment of TB used in the TRiAD study

Grade	Severity Rating	Definition
Grade 1	Mild	Transient or mild discomfort (< 48 hours); no medical intervention/therapy required. The participant will be followed carefully and the study drugs will be continued
Grade 2	Moderate	Mild to moderate limitation in activity - some assistance may be needed; no or minimal medical intervention/therapy required. The participant will be followed more closely, with additional laboratory and/or clinic visits as necessary; treatment should be continued unless in the view of the clinician/investigator this would be unsafe.

Grade 3	Severe	Marked limitation in activity, some assistance usually required; medical intervention/therapy required, hospitalizations possible.
Grade 4	Potentially life threatening	Extreme limitation in activity, significant assistance required; significant medical intervention/therapy required, hospitalization or hospice care probable.
Grade 5	Fatal	Death

An AE **does not** include:

- Pre-existing diseases or conditions present or detected prior to start of study drug administration that does not increase in grade. All pre-existing conditions (grade 3 or higher) must be clearly documented on the enrolment CRF. If the frequency, intensity, or the character of the condition worsens to grade ≥ 3 level during the reporting period, the event should be defined as an AE;
- Medical or surgical procedures (e.g. Surgery, endoscopy, tooth extraction, transfusion); the condition that leads to the procedure is an adverse event;
- Situations where an untoward medical occurrence has not occurred (e.g. Hospitalization for elective surgery, social and/or convenience admissions).

The PI or designee must determine the relationship of the AE to the drugs under investigation and document on the appropriate CRF (AE Form). For each AE, an assessment of the relatedness to the study drug will be made using the WHO criteria:

Probable: The event is an identifiable clinical or laboratory-linked phenomenon; the time elapsed between the administration of the drug and the occurrence of the event is plausible; the event cannot be explained by concurrent disease or any other drug or chemical; the participant recovered within a plausible length of time following withdrawal of the drug; re-challenge did not occur, or the result is unknown.

Possible: The time elapsed between the administration of the drug and the occurrence of the event is plausible; the outcome of withdrawal of the suspect medicine is not known, and/or the medicine might have been continued and the final outcome is not known; and/or there might be no information on withdrawal of the medicine; and/or the event could be explained by concomitant disease or use of other drugs or chemicals; and/or there might be no information on the presence or absence of other medicines.

Unrelated (Unlikely): The event occurred with a duration to onset that makes a causal effect improbable with the drug being considered; and/or the event commenced before the first administration of the drug; and/or the drug was withdrawn and this made no difference to the event when, clinically, recovery would be expected; and/or it is strongly suggestive of a non-causal relationship if the drug was continued and the event resolved. This category has also been referred to as doubtful.

All AEs will be captured regardless of the association or otherwise to the study product and reported on the AE CRF in accordance with study specific procedures. All AE reports will contain at least the date the AE occurred, a brief description of the event, the relationship to

study drug, the study drug action taken, the outcome, date resolved, and the seriousness of the event.

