4.5. Study Outcome Measures

Primary Outcomes:

- Time to initiation of resistance-pattern appropriate TB treatment from the date of first sputum collection
- Proportion of participants with favourable treatment outcome as defined in section 9.3

Secondary Outcomes:

- Incidence of adverse drug reactions documented during all-oral treatment under operational conditions (cohort 1 and 2)
- All-cause mortality for the duration of treatment and follow-up (cohort 1 and 2)
- Time to sputum (culture) conversion (cohort 1 and 2)
- Prevalence of HR-TB (cohort 1)
- Prevalence of XDR-TB (cohort 2)
- Proportion of participants with BDQ and LZD resistance not eligible for short-course treatment
- Clinical utility and feasibility of TB-MBLA for bacteriological follow-up in DR-TB treatment (assessment of viable bacterial load trajectories in response to treatment) (cohort 1)
- Accuracy and quality of Xpert XDR testing (cohort 1 and 2)
- Additional resistance to new and repurposed drugs (cohort 1 and cohort 2)
- Cost effectiveness (cost per person tested and incremental cost per DR-TB participant timely initiated on appropriate treatment) (cohort 1 and 2)
- Feasibility and acceptability of participant triaging (participant, health care provider and policy makers' perspective) with enablers and barriers for implementing the algorithm (cohort 1 and 2)
- Operational feasibility of Xpert XDR testing (infrastructure and human resource requirements) (cohort 1 and 2)

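### The ADR definition takes in lack of efficacy, so the ADR incidence outcome can mix toxicity with treatment failure

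*Protocol*

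**What the plan says.** - **Definition (section 10.1).** An ADR is a response to a medicine that is "noxious and unintended, including lack of efficacy". The next sentence adds that AEs judged by the investigator as "having a reasonable causal relationship to a medicinal product qualify as adverse reactions". The paragraph ends: "ADRs that occur following enrolment will be considered AEs and will be recorded on the AE CRF".
- **Recording (section 10.1).** "Clinical AEs grade 3-5 will be recorded via the AE recording CRF". Later the same section says that all AEs are captured whatever their relation to the study product.
- **Safety outcome (section 4.5).** The secondary outcomes open with "Incidence of adverse drug reactions documented during all-oral treatment under operational conditions (cohort 1 and 2". The list is not ranked.
- **Treatment outcome (sections 4.5 and 9.3).** The second primary outcome is "Proportion of participants with favourable treatment outcome as defined in section 9.3". In Table 7, the grounds for treatment failure in the protocol's own column include "lack of conversion by the end of the intensive phase, or" and, as a separate item, ADRs.
- **Analysis (section 9.2).** Proportions with AEs and with serious AEs are planned for both cohorts, stratified by type of DR-TB, regimen and HIV status. No separate ADR analysis is described.
- **Treatment changes (section 8.1).** Lack of effectiveness is one listed reason for interrupting the regimen. A change of treatment is notified to the coordinating centre on an SAE form.

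**The concern.** A safety outcome should measure harm from the drugs, and an efficacy outcome should measure whether the disease was controlled. Section 4.4.1 sets both as objectives for the all-oral regimens. If the ADR definition also takes in lack of efficacy, one participant with resistant disease that does not respond can appear in both, with no toxicity at all. ADR incidence then no longer tells a reader how well the regimens are tolerated.

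Consistency is also at stake. The protocol covers 13 sites in three countries. Some investigators will apply the definition as written and record a clinical failure as an ADR. Others will follow the separation in Table 7 and record it only as a treatment outcome. Differences in ADR incidence between sites could then reflect coding. Section 9.2 plans an interim analysis of the safety outcomes to inform policy makers, so an ambiguous count could be reported before the end of the study.

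**Working it through.** The protocol gives no figure that depends on this definition, so there is nothing to reproduce. The check is to follow the definition through the document.

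1. **Does the wording take in efficacy failure?** Yes. Section 10.1 names lack of efficacy as part of the ADR definition.
2. **Does it reach the data?** Yes. ADRs after enrolment become AEs on the AE form.
3. **Does it reach a named outcome?** Yes. Section 4.5 lists ADR incidence for both cohorts, and section 4.4.1 has a related objective on drug-related AEs.
4. **Does anything take it out again?** No. Section 10.1's list of what an AE does not include covers pre-existing conditions, procedures, and situations with no untoward occurrence. It does not mention non-conversion, reversion or failure. Section 10.2 names hospital admission for respiratory symptoms as an expected disease-related event. However, it only waives regulatory reporting and removes nothing from a count.
5. **Which cases could pass the recording conditions?** The conditions are the investigator's causality judgement, the grade threshold (3 to 5 in section 10.1; solicited grade 3 and 4 in the notes to Table 3), and severity graded by limitation of activity (Table 8). A positive culture without symptoms would not obviously pass. A failure with marked symptoms, or one the investigator attributes to the medicine, could. The threshold is not watertight, because section 10.1 also says that all AEs are captured and that grading is subjective.
6. **Is the definition used consistently?** No. Table 7 lists lack of conversion and ADRs as separate grounds, and section 8.2 separates severe toxicity, treatment failure and drug resistance. Those passages treat an ADR as toxicity; section 10.1 does not.

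**How many could be affected?** The protocol states no failure rate. Its success proportions in section 9.1 give only a loose ceiling for treatment failures in cohort 1:

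- At the historical average of 63%: 880 × (1 − 0.63) = 325.6, about 326 participants without success.
- At the detectable target of 85%: 880 × (1 − 0.85) = 132 participants without success.

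Both numbers also contain deaths, loss to follow-up and participants not evaluated. Only failures that pass step 5 could enter the ADR count, so the true number is smaller and cannot be derived. Recurrence after successful treatment lies outside this ceiling, and cohort 2 is not included.

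**The case against.** The strongest reply is that no sentence tells sites to record non-conversion or failure as an ADR. The phrase sits inside a definition that requires a noxious response to a medicine, followed by a causality judgement. Wherever the protocol uses the two ideas, it keeps them apart. This stands in part: a reader might infer that every treatment failure counts as an ADR, and the document does not support that. It does not answer the narrower point that some failures can qualify and none is excluded.

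A second reply is that section 9.2 analyses AEs and serious AEs, not ADRs. The AE definition covers any untoward occurrence, so clinical deterioration from TB may be an AE with or without the phrase. This also stands. The point is therefore confined to ADR incidence and to any tabulation of drug-related events.

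A third is that counting conventions belong in the statistical analysis plan, which is not shown. That would hold if the protocol were silent. Here the protocol itself fixes a definition and attaches a listed outcome to it.

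A reader might also infer that the primary treatment outcome is affected through the ADR ground in Table 7. Non-conversion that leads to the specified treatment change is already failure on its own ground. An earlier change for poor response could fall under the ADR ground only by carrying the section 10.1 wording into a table that separates the two. That is a reason to make the wording explicit, not evidence that the primary outcome is wrong.

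**Conclusion.** The point holds as a defect of definition with limited reach. As written, ADR incidence can include efficacy failures that are symptomatic or attributed to the medicine, and sites can reasonably differ on whether to include them. ADR incidence is one unranked secondary outcome, so it should not be called the main safety outcome.

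Two stronger readings should not be drawn. The first is that the distortion falls most heavily on BPaL because it is given for more resistant disease. The protocol gives no failure rates by regimen, and section 2.3.1 cites 90% favourable outcomes for BPaL, so no direction follows.

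The second is a specific size. Suppose 20% toxicity ADRs, independence, and failure proportions f of 2% or 10%. The reported proportion is then 1 − (1 − f)(1 − 0.20), which gives 21.6% or 28.0%, a gap of 6.4 points. All of these inputs are assumptions, and the sum counts every failure as an ADR, so it is an upper bound for those inputs and not an estimate for this study.

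Sample size and power are unaffected.

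**What to change.** Keep the section 10.1 definition for safety reporting if a regulator requires it, and add a statement on counting. It should say that lack of efficacy (non-conversion, reversion, treatment failure, recurrence) is not counted as an ADR for:

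- the ADR incidence outcome in section 4.5;
- any tabulation of ADRs or drug-related AEs under section 9.2;
- the ADR ground for treatment failure in Table 7.

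These events are reported as treatment outcomes under section 9.3. If one is recorded on the AE form, it is tabulated as a separate category. Section 8.1 should say how an SAE form submitted only to notify a treatment change for lack of effectiveness is classified in the safety data.

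The cost is a few sentences, one extra category on the AE form, and a slightly lower reported ADR incidence. No treatment rule changes.
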